The study is to be performed in Hong Kong, with subjects aged 11-14 studying Form 1 and 2 in secondary school being recruited. Recruitment and cognitive testing will take place at the secondary school, whilst physician follow up and skin prick tests will take place at Prince of Wales Hospital. Healthy individuals as well as patients with a history of allergic rhinitis will be recruited. Chinese will be the main language used. The total number of the Form 1 students within the school will be around 200. The estimated participation rate will be approximately 70%. As the prevalence of allergic rhinitis in Hong Kong children under the age of 14 is approximately 24.5%[1], the expected number of participants and students with allergic rhinitis are 140 and 34 respectively.

STUDY FUNDING

Study funding will be sourced from Department of Otorhinolaryngology, Head and Neck Surgery (ENT), Faculty of Medicine, The Chinese University of Hong Kong (CUHK).

ETHICAL CONSIDERATIONS

Ethical approval will be sought from The Joint Chinese University of Hong Kong - New Territories East Cluster Clinical Research Ethics Committee (CUHK-NTEC CREC). Legal guardians will be well-informed as to the nature of the study and if necessary, the medication treatment and possible side effects. Invitation letter (Appendix 1) will be sent and written consent (Appendix 2) will be obtained from willing participants in the study. Confidentiality of all personal data, including questionnaire responses, will be kept in accordance with the Hong Kong Privacy Ordinance. Names and other identifying information will be omitted from the electronic database. All computer records will be locked with a password. Subjects will be withdrawn from the study immediately if his/her legal guardian chooses to withdraw consent. Files will be locked in the cabinets and will only be assessed by authorized research staff.

PRECAUTIONS TO PROTECT SUBJECTS

As subjects are under the age of 18, the subjects and legal guardians will be fully informed of the nature, scope, and possible consequences of the study. This study presents no greater than minimal risk to children and their safety and welfare are of utmost importance. Legal guardians have the right to withdraw subjects from the program at any time. Standard treatment for allergic rhinitis will be prescribed by physician according to guidelines. If issues arise, research staff will be available for subjects to contact during office hours.

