MATERIALS AND INVESTIGATIONS USED

Rhinitis Symptom Utility Index (RSUI)

The RSUI is a preference-weighted measure of common rhinitis-related symptoms presented in a 10-item questionnaire (Appendix 4). Five rhinitis-related symptoms (stuffy or blocked nose, runny nose, sneezing, itchy eyes, and itchy nose or throat) are assessed with a 4-point Likert scale in terms of their frequency and severity during the past 14-day period. Frequency of each symptom is judged as either “not at all”, “1-3 days”, “4-7 days”, or “8-14 days”. Severity of each symptom is evaluated as “not applicable”, “mild”, “moderate” or “severe”. RSUI is the utility of the symptom state on a scale where the best state (no symptoms) has a score of 1 and the worst possible state (severe symptoms for 8 to 14 days) has a score of 0. ^[8]

Digit Span Test (DST)

Digit Span Tests are commonly seen in the Wechsler tests for intelligence. The current version used is a modified version by Lee and King (2010) ^[9], with higher ceiling and simplified administration to Final Version (Dated on 11 April 2018)

prevent exhaustion. There are two parts of the test: forward span and backward span. Forward span serves to assess auditory sustained attention, whereas backward span tests for the participant's working memory. In the forward span test, participants listen to a series of number digits and repeats the sequence of numbers heard. The digit series will increase in length by 1 after each successful trial until the subject fails to repeat the series in its entirety. In the backward span test, the subject listens to a series of numbers, but repeats the numbers in reverse sequence. Alike the forward span test, the digit series will increase in length by 1 after each successful trial until the subject fails to recall the sequence in its entirety. The digit span test is a well-established test for the pediatric population, with multiple studies utilizing it as an assessment of working memory in children. ^[10]

Stroop Test (Chinese Translated Victoria Version)

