Students aged 11 to 14 currently studying Form 1 and 2 in secondary school will be recruited directly through invitation. Recruitment will include patients suffering from untreated allergic rhinitis in addition to healthy individuals to serve as a control group. Patients suffering from allergic rhinitis will be classified according to ARIA guidelines into mild/moderate/severe, and duration into intermittent/persistent. Patients suffering from rhinitis due to non-allergic origins or those associated with nasal polyposis or sinusitis will be excluded. Patients are going to complete the Rhinitis Symptom Utility Index (RSUI) questionnaire for assessing pre and post symptoms.

Control Group- Inclusion Criteria

1. Both genders of 11-14 years
2. Chinese in ethnicity
3. Subjects who have not been diagnosed with a long term medical or psychiatric problem
4. Subjects who are not currently undergoing any long term medical treatment.

Patient Group- Inclusion Criteria

1. Both genders of 11-14 years, diagnosed with allergic rhinitis on basis of screening instruments, medical history, clinical assessment (by general ORL examination including nasal endoscopy)
2. Chinese in ethnicity
3. Positive skin prick test with wheal diameter $\geq 3\text{mm}$

4. Ability to understand the nature, scope, and possible consequences of the study
5. Capability and willingness to comply with the requirements of the protocol

Patient Group- Exclusion Criteria

1. Subjects with co-existing nasal conditions other than AR, which may affect nasal pathology (nasal polyposis, sinusitis, severe deviations of nasal septum, tumors of the nasal cavity, acute/chronic rhinosinusitis or any underlying pathology that might affect nasal breathing or nocturnal sleep)
2. Subjects with prior nasal surgery (e.g. nasal cavity, sinuses)
3. Subjects with known brain disorders, prior brain surgery or history of stroke
4. Subjects diagnosed with learning disability, autism or attention deficit hyperactivity disorder (ADHD)
5. Subjects with history of known sleep disorder, central or obstructive sleep apnea, narcolepsy, insomnia, patients requiring regular sleep medication and those hypersensitive to applied topical nasal steroids
6. Subjects who have taken topical nasal steroids, oral anti-histamines or medications affecting nasal symptoms 30 days prior to commencement of study
7. Subjects with hypersensitivity reactions towards topical nasal steroids or oral anti-histamines

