8. Subjects previously diagnosed with any psychiatric disorders
9. Subjects who suffered from a respiratory tract infection within the past 30 days
10. Subjects who have clinically major cardiovascular, respiratory, hepatic, neurological, endocrine, immunological or other major systemic disease(s)
11. Subjects who are undergoing a long-term medical treatment plan

TREATMENT AND COMPLIANCE

Medication (complying with standard treatment guidelines) will be prescribed to the patient group. As this study does not investigate the efficacy of a specific drug, the medication plan will be up to the discretion of the attending physician with the aim of alleviating nasal symptoms. Commonly, pediatric allergic rhinitis treatment involves topical nasal steroids and 2nd generation antihistamines. Compliance will be monitored via the treatment diary, phone call after four weeks of treatment, and pill counting. Should issues arise anytime during the study, research staff will be available for subjects to contact during office hours. To increase the incentives of the participants, reinforcement programs, such as hospital visits and a health-related seminar, will be held. Each participant will receive a certificate upon completion.

METHOD OF ANALYSIS

Multilevel models, the mixed effects models [19], will be used to compare the longitudinal rate of change on cognitive function and different areas of cognitive function (as measured by Digit Span Test, Stroop Test, Chinese Auditory Verbal Learning Test, Verbal Fluency Test, and Trail Making Test) both within and between normal and allergic rhinitis patients. Multilevel models are random effects models that take into account the hierarchical nature of the data, and the within- and between-subject heterogeneity [20]. For longitudinal data, such models allow for measurements made at unequal intervals and with a varied number of measurements (i.e. subjects who may have one or several measurements). The models are fitted by the method of restricted iterative generalized least-squares algorithm of MLn for Windows software package, Version 2.0 (Institute of Education, University of London, London, UK). The likelihood ratio test is used to assess the statistical significance of the estimates at the 5% level. The model assumptions are checked by inspection of the standardized residuals for normality and constant variance.

PROPOSED TIMELINE

Week 0

- A. Consent will be sought from potential subjects

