- B. Screening questionnaires (based on the ARIA and ISAAC questionnaires) will be given to the parents of the subjects as a preliminary assessment of the subject's condition
- C. Pre-treatment RSUI questionnaire will be given and explained to those suspected to suffer from allergic rhinitis.

Week 1

- A. Subjects who are suspected to suffer from allergic rhinitis will undergo a skin prick test to exclude the possibility of non-allergic rhinitis.
- B. Subjects who are suspected to suffer from allergic rhinitis will then be assessed by ENT specialist to perform screening of individual's eligibility for participation in the study on the basis of medical history, clinical assessment including general ORL exam and nasal endoscopy to exclude any physical obstructions in the nasal cavities that might affect nasal breathing or nocturnal sleep.
- C. Inclusion and exclusion criteria will be checked
- D. Patients diagnosed to suffer from allergic rhinitis will be prescribed a personalized medical treatment which is to begin when instructed 1 week later.

Week 2

- A. Subjects undergo cognitive testing (Digit Span Test, Stroop Test, Chinese Auditory Verbal Learning Test, Verbal Fluency Test, and Trail Making Test)
- B. Subjects are instructed to begin personalized medical treatment the day after cognitive testing.
- C. Patients are reminded not to use over-the-counter drugs or prescription medications that could affect rhinitis symptoms during the treatment period and to record any medications they take.

Week 6

Reminder calls to continue treatment plan and treatment diary to ensure compliance

Week 10

- A. End of treatment plan.
- B. All unused drugs will be collected to check for compliance
- C. Subjects undergo cognitive testing (Digit Span Test, Stroop Test, Chinese Auditory Verbal Learning Test, Verbal Fluency Test, and Trail Making Test)
- D. Subjects complete post-treatment RSUI questionnaire
- E. Subjects presented with completion certificate

REFERENCES

1. New Publication by HKU Paediatricians : 'Allergic Rhinitis – The Paediatric Disease You Must Learn' - All News - Media - HKU. (n.d.). Retrieved October 10, 2017, from http://www.hku.hk/press/news_detail_6527.html
2. Aetiology of allergic rhinitis in Hong Kong. (2015, March 19). Retrieved October 10, 2017, from <http://www.sciencedirect.com/science/article/pii/S1323893015315343>

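### The only scheduled pre-treatment RSUI is handed out at Week 0 with no stated completion time, so the secondary outcome's baseline may fall up to about two weeks before treatment starts (low severity)

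*Combined protocol and SAP*

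**What the plan says.** BRIEF SUMMARY OF STUDY names the RSUI in patients as the secondary outcome. SUBJECTS AND METHOD gives its purpose: "Patients are going to complete the Rhinitis Symptom Utility Index (RSUI) questionnaire for assessing pre and post symptoms". The description of the instrument says that symptom frequency and severity are rated "during the past 14-day period".

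PROPOSED TIMELINE sets the order of events:

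- Week 0: "Pre-treatment RSUI questionnaire will be given and explained to those suspected to suffer from allergic rhinitis".
- Week 1: skin prick test, specialist assessment and check of eligibility. Then "Patients diagnosed to suffer from allergic rhinitis will be prescribed a personalized medical treatment which is to begin when instructed 1 week later".
- Week 2: cognitive testing. Then "Subjects are instructed to begin personalized medical treatment the day after cognitive testing".
- Week 10: end of treatment, second cognitive testing, and "Subjects complete post-treatment RSUI questionnaire".

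No RSUI is listed at Week 1 or Week 2. The Week 10 form is tied to a visit. For the Week 0 form the timeline fixes when it is issued, but not when it is filled in or returned.

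METHOD OF ANALYSIS uses multilevel models to "compare the longitudinal rate of change on cognitive function and different areas of cognitive function" and names the five cognitive tests. It does not define an RSUI baseline.

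**The concern.** A before-and-after symptom score is easiest to read when the first measurement sits immediately before treatment. Here the cognitive baseline does, because it is taken the day before the first dose, but the RSUI baseline need not. If a child fills in the form when it is issued, the score describes the two weeks before Week 0 and none of the two weeks before the Week 2 session. If children return it at different times, the baseline window differs between them.

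The form goes to children because rhinitis is suspected, and rhinitis symptoms vary from week to week. Some change between Week 0 and Week 2 is therefore possible without treatment, either as ordinary fluctuation or as regression to the mean. A single pre-treatment value per child cannot separate that change from change during treatment. What is at stake is the interpretation of the secondary outcome.

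**Working it through.** **Inputs.** Weeks of the events: PROPOSED TIMELINE. Recall of 14 days: the RSUI description. Treatment of 8 weeks: RESEARCH OBJECTIVES. Expected numbers: STUDY SAMPLE AND SETTING.

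**The plan's own figures.** 200 × 0.70 = 140 participants; 140 × 0.245 = 34.3, so 34 patients; 140 − 34 = 106 controls. This agrees with the statement that "the expected number of participants and students with allergic rhinitis are 140 and 34 respectively". Week 10 − Week 2 = 8 weeks = 56 days, which matches the stated treatment period.

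**Baseline window.** Take Week w as day 7w. The Week 2 session is day 14, the first dose day 15 and the Week 10 visit day 70. A form completed on day d (0 ≤ d ≤ 14) has these properties:

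- recall window: day d − 14 to day d
- days covered out of the 14 before the Week 2 session: d
- days from completion to first dose: 15 − d
- days from completion to the Week 10 form: 70 − d

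| Completed | d | Recall window (days) | Covered, of 14 | Days to first dose | Span to Week 10 | Untreated share of span |
|---|---|---|---|---|---|---|
| Week 0 | 0 | −14 to 0 | 0 | 15 | 70 | 15/70 = 21% |
| Week 1 | 7 | −7 to 7 | 7 | 8 | 63 | 8/63 = 13% |
| Week 2 | 14 | 0 to 14 | 14 | 1 | 56 | 1/56 = 2% |

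Only completion at the Week 2 session gives an RSUI interval equal to the 56 days of treatment and of cognitive follow-up.

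**Does anything else in the plan fill the gap?**

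- The baseline TNSS is part of the screening questionnaire, which is also given out at Week 0.
- The treatment diary is kept to check compliance and is expressly not used to interpret outcomes.
- Controls receive no pre-treatment RSUI, so untreated drift cannot be estimated from them.
- The multilevel models accept unequal intervals, but the section describes them for the cognitive tests. Accepting unequal intervals also does not separate change before treatment from change during it when each child has one pre-treatment value.

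**Size of any shift.** The documents give no RSUI standard deviation, no correlation over time and no fraction of children flagged by screening. The shift therefore cannot be calculated from them.

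**The case against.** The strongest case on the other side is that the harm is hypothetical. The form may in practice come back shortly before the Week 2 session, in which case the gap is one day. The RSUI is not the screening instrument. Diagnosis also rests on history, endoscopy and skin prick test, and children with a respiratory infection in the past 30 days are excluded, which removes one common source of passing symptoms. A Week 0 form also has a merit: it comes before diagnosis and prescription, so labelling cannot influence it. And this is one secondary, patient-only measure in a pilot.

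Most of this stands, and it is why the severity is low. It does not remove the point, because a plan that leaves completion anywhere between Week 0 and Week 2 has not defined its baseline.

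A reader might infer more than the documents support:

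- *That the form is undated.* The body text sets no completion time, but the RSUI form is an appendix that is not in the available text and may carry a date field. A date field would record when the form was completed; it would not fix that time.
- *That the RSUI change is biased.* This is a risk and has not been shown.
- *That the cognitive comparison is compromised.* It is not. Its baseline is taken the day before treatment starts.
- *That a better-timed RSUI would let the study attribute cognitive gains to symptom relief.* It would not. There is no untreated rhinitis group, so natural remission, season or extra clinic contact could also explain a larger gain in patients.

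**Conclusion.** The point holds as a low-severity weakness in the timing of a secondary outcome. As written, the RSUI baseline may cover anywhere from 0 to 14 of the 14 days before the Week 2 session. The RSUI change may span 56 to 70 days, of which 1 to 15 are untreated. These figures rest on counting weeks as exact multiples of seven days and on completion no later than the Week 2 session. Whether the RSUI change is shifted, and by how much, cannot be derived from the documents; the shift could be zero.

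A separate wording point arises from the design and not from the timing. RESEARCH HYPOTHESIS attributes the expected larger cognitive gain in patients to relief of nasal symptoms. Without an untreated rhinitis group, such a gain can be reported only as an association with the treatment period. The study's title and summary already speak of association.

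**What to change.** 1. Have patients complete the RSUI at the Week 2 session, after the cognitive tests and before treatment starts. The order matters: symptom questions put only to patients should not come before the primary outcome.
2. Define the Week 2 form as the RSUI baseline, and report the mean Week 2 to Week 10 change in patients with a 95% confidence interval.
3. Keep the Week 0 form as a screening value, record its completion date, and report the Week 0 to Week 2 difference descriptively.
4. Word the conclusion on cognition as an association with the treatment period.

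**Cost.** One extra 10-item form for about 34 patients at a session already scheduled, one recorded date and a few lines of text. No new visit and no change to treatment.

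**Downsides.** The Week 2 form follows diagnosis, so labelling may affect it, and the Week 0 to Week 2 difference may reflect labelling or repeat administration as well as drift. If the Week 0 form is returned d days late, the two recall windows overlap by d days. Drift is reduced but not removed. The study period opens on 1 December 2017 and this version is dated 11 April 2018, so some baselines may already have been collected. For those children, the completion date of the existing form should be recorded where it is known, and their RSUI change reported separately.

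### The one scheduled contact during treatment is a compliance reminder, and no step in the body text asks patients about side effects or why treatment was changed or stopped

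*Combined protocol and SAP*

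**What the plan says.** Treatment and Compliance leaves the drug choice to the attending physician and adds: "Commonly, pediatric allergic rhinitis treatment involves topical nasal steroids and 2nd generation antihistamines". On monitoring it says: "Compliance will be monitored via the treatment diary, phone call after four weeks of treatment, and pill counting". The remaining route is one that the family must start: "Should issues arise anytime during the study, research staff will be available for subjects to contact during office hours".

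In the Proposed Timeline, the specialist assesses and prescribes at Week 1, and treatment starts the day after the Week 2 cognitive tests. The Week 6 entry reads in full: "Reminder calls to continue treatment plan and treatment diary to ensure compliance". At Week 10 treatment ends, unused drugs are collected as a compliance check, and the cognitive tests and the RSUI are repeated.

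Study Sample and Setting mentions a further medical contact, giving its place only: "whilst physician follow up and skin prick tests will take place at Prince of Wales Hospital".

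Side effects of treatment are named under Ethical Considerations, where guardians are to be informed about, "if necessary, the medication treatment and possible side effects". Precautions to Protect Subjects states: "This study presents no greater than minimal risk to children and their safety and welfare are of utmost importance". The exclusion criteria remove "Subjects with hypersensitivity reactions towards topical nasal steroids or oral anti-histamines".

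**The concern.** The study finds children with untreated allergic rhinitis through a school, has drugs prescribed for them, and sets the contact schedule. Followed as written, the one mid-treatment contact tells the child to carry on and does not ask how the drug is tolerated. Apart from any undated physician follow-up or a prompt on the diary form, a side effect reaches the study mainly if the child adds a remark to the diary, the family mentions it on the call, or the family contacts staff in office hours.

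The same gap affects what is known about adherence. Dose times, pill counts and the instruction to note other medications can show that a drug was stopped or added. They do not ask why, so a child who stopped because of drowsiness may look the same as one who forgot.

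What is at stake is the welfare of children on treatment, and a plain descriptive account of how treatment was tolerated.

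**Working it through.** The plan states no figure on this point, so the check is a reading of each scheduled step, with the timing confirmed by arithmetic.

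**Timing.** Treatment runs from the day after Week 2 testing to Week 10: 10 − 2 = 8 weeks, which agrees with the research objectives. The call comes at 6 − 2 = 4 weeks into treatment, which agrees with Treatment and Compliance.

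**Steps from the prescription onward.**

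| Step | Described content | Asks about side effects or reasons for change or stop? |
|---|---|---|
| Week 1, physician | Eligibility assessment, prescription | Before treatment, so not applicable |
| Week 2, school | Cognitive tests; start instruction; reminder to avoid other rhinitis drugs and record any medication | No |
| Daily diary | Dose time, optional remarks; stated to be for compliance | No item described |
| Week 6, call | Reminder about treatment and diary | No |
| Week 10 | Drug return for compliance, cognitive tests, RSUI, certificate | No |
| Physician follow-up, hospital | Place only | Not stated |

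The RSUI section lists five rhinitis symptoms, each rated for frequency and severity, so it does not cover drug side effects. The hospital visits named under Treatment and Compliance are offered as an incentive, and are not described as clinical follow-up.

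**Count.** Contacts dated in the timeline within the treatment period: 1 (Week 6). Contacts at its end: 1 (Week 10). Of these two, 0 include a question on side effects or on reasons for changing or stopping. Physician contacts dated after Week 1: 0.

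**Two limits on that count.** The follow-up in Study Sample and Setting may be a later visit, or may refer only to the Week 1 assessment; the text does not settle it. Appendices 2 (consent) and 5 (diary) were not available, so the count applies to the body text alone.

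**The case against.** The strongest reply is that follow-up ordinarily means contact after a first assessment. It is listed separately from the skin prick tests, and a physician with discretion over the medication plan would usually see the child again. The diary is the form patients fill in every day, so it is a likely place for a side-effect prompt. Both points stand, and they limit the claim to what the body text shows.

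Much is also handled already. Treatment follows standard guidelines, known hypersensitivity and major systemic disease are exclusions, guardians are told of possible side effects and may withdraw the child at any time, and staff contact is offered in three places. These lower the risk. None is a question put to a child on treatment.

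Three stronger readings are tempting, and the documents support none of them.

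- **Unmonitored exposure.** A reader might infer 34 × 8 = 272 child-weeks without a side-effect question. That fails if the undated follow-up or the diary includes one. The 34 is 24.5% of 140 participants (0.245 × 140 = 34.3), not reduced for skin-prick confirmation or the eleven exclusion criteria.
- **Near-certain harm.** If 5% to 15% of 34 children had a side effect, 1.7 to 5.1 would be affected, and the chance of at least one would be 1 − 0.95^34 = 0.83 to 1 − 0.85^34 = 0.996. The rate is an assumption with no source in the documents, and one mild event counts. The result is not evidence of harm.
- **A compromised cognitive comparison.** Suppose each affected child scored 0.5 SD lower at Week 10 (assumed). The patient mean would move by 0.05 × 0.5 = 0.025 to 0.15 × 0.5 = 0.075 SD. The standard error of the difference in change is √(2(1 − r)) × √(1/34 + 1/106), or 0.233, 0.197 and 0.125 SD at assumed test-retest correlations r of 0.3, 0.5 and 0.8. The shift is then 0.11 to 0.60 standard errors (0.025/0.233 to 0.075/0.125), below one throughout.

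Two objections shape the remedy. A Week 10 question cannot protect a child whose treatment has ended. And questions on drowsiness put only to patients before a cognitive test could prime them and not the controls on the primary outcomes.

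**Conclusion.** The point holds as a minor safety improvement. In the body text, one dated contact falls within 8 weeks of treatment, it is a compliance reminder, and no listed step asks about side effects or about reasons for changing or stopping. This rests on the text alone and needs no assumed rate. It does not show that no prompt exists, since the physician follow-up is undated and the diary form was not available. No stated number, primary analysis or conclusion of the plan is affected.

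**What to change.** 1. At the existing Week 6 call, ask each patient or guardian two fixed questions: any side effect, including drowsiness; and any change or stop in the prescribed treatment, with the reason. Record the answers and pass positive ones to the attending physician, who decides on care.
2. Repeat the questions at Week 10, only after cognitive testing is complete, and report the answers descriptively. This serves description, not protection during treatment.
3. Do not add a drowsiness question at Week 2 before testing. If a pre-treatment answer is wanted, because the Introduction says the disease itself causes daytime sleepiness, ask it after that session's tests.
4. State when the physician follow-up takes place and that side effects found there are recorded. If it means only the Week 1 assessment, say so. If the diary already carries a prompt, say that too.

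Cost: at an assumed 3 minutes per contact, 34 × 3 = 102 minutes (1.7 staff hours) for Week 6 alone and 34 × 6 = 204 minutes (3.4 hours) with Week 10. An optional 1 minute at Week 2 brings it to 34 × 7 = 238 minutes, about 4.0 hours. The physician will have a few reports to handle, and some will not be due to the drug. The first four weeks of treatment would still rely on families reporting problems themselves, unless the physician follow-up falls there or the diary already asks.
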